# 1. Background and Rationale

Kidney transplantation is the preferred treatment for end-stage renal disease (ESRD) patients and is associated with increased quality of life and reduced mortality compared with dialysis. Nearly 17,000 kidney transplants are performed in the United States annually, and despite advances in improving early post-transplant outcomes, the need to improve long-term outcomes remains an important goal. Long-term immunosuppressive therapy is necessary to prevent rejection, but toxicity associated with immunosuppressive therapy can ultimately lead to decreased renal function and result in the need for re-transplantation. Traditional immunosuppressive regimens for kidney transplant consist of the calcineurin inhibitors (CNIs) cyclosporine A (CsA) and tacrolimus. These agents are associated with long-term renal toxicity and increase cardiovascular risk factors, including diabetes mellitus, hypertension, and hyperlipidemia.

The development of belatacept (trade name Nulojix), a member of a novel class of immunosuppressive medications known as selective T-cell costimulation blocking agents, represents a major advance in targeted immunosuppressive therapy. Immunosuppressive therapy with belatacept has been shown to improve renal function and has a favorable metabolic profile compared with CNIs. The mechanism of action of belatacept is more selective than that of previous immunosuppressants and its effect more specific; in animal models, belatacept more effectively blocks humoral responses that can lead to chronic injury and renal failure. During the Belatacept Evaluation of Nephroprotection and Efficacy as First-line Immunosuppression Trial (BENEFIT), the overall incidence and severity of acute rejection was higher in patients treated with belatacept compared to the CsA treatment group; however, renal function as measured by the calculated glomerular filtration rate (cGFR) was up to 10 cc/min higher in the belatacept treatment group, which suggests that long-term graft survival and renal function may be improved compared to CsA (Vincenti F. et al AJT 2012).

Belatacept immunosuppressive therapy was implemented in the Emory Transplant Center (ETC) beginning in August of 2011. Current dosing protocol requires post-transplant kidney patients who are treated with belatacept to receive an infusion every 1 month, which presents logistical challenges due to the high cost of infusions, the limited capacity of the sites administering infusions, and inconvenience to patients. Definitive clinical evidence is lacking for equivalent treatment outcomes for patients who receive infusions at one month (q-1M) intervals versus every two month (q-2M) intervals. Data from five year (Vincenti F, Blancho G, Durrbach A et al. J Am Soc Nephrol 2010) and ten year (personal communication, [name]) follow up of the phase II clinical studies suggest that there are no significant differences in the patient outcomes for q-1Mversus q-2 Mdosing intervals. However, conclusions regarding differential

outcomes for the dosing interval regimens were limited by small sample size and deserve further investigation.

We hypothesize that immunologically low risk patients who are stable on belatacept therapy at least one year post transplant can be safely transitioned from an every 1 month to an every 2 months belatacept schedule, without a decrease in renal function or an increase in acute rejection. The Emory Transplant Center is uniquely qualified to perform this every two month study. We perform approximately 230 kidney transplants per year, utilizing belatacept as standard therapy in all eligible patients (Epstein Barr Virus (EBV) positive, etc). We have performed almost 500 kidney transplants on patients using belatacept as the primary immunosuppressant medication between August 2011 and the present (May 2015). Based on this clinical volume and high rate of belatacept use, we propose to screen approximately 18 patients per month and estimate enrolling an average of 12 patients per month into the study, specifically converting 6 patients per month from a q-1 month to a q-2 month schedule.

# 2. Study Objectives

# 2.1 Primary Objective

The primary objective of this non-inferiority trial involving immunologically low-risk patients is to show that the GFR 12 months post-randomization is the same for patients who receive belatacept at q-4 and q-8 dosing intervals.

# 2.2 Secondary Objective

- Assessing the incidence and severity of acute rejection 6 and 12 months post randomization
- Assessing the total cost associated with q-1M and q-2M dosing intervals
- Assessing the incidence of infection in the q-1M and q-2M patient groups
- Assessing the incidence of death and graft loss at 6 and 12 months
- Assessing the incidence of human leukocyte antigen (HLA) antibodies at randomization and at 6 and 12 months
- Assessing the frequency of clinic visits, hospitalizations, and transplant biopsies in the two patient groups

# 3. Assessment of Efficacy

### 3.1 Primary Outcome Measure

This study will compare the primary outcome of mean eGFR between the standard q-1M control group and the q-2M treatment group, with the hypothesis that mean eGFR will not vary between the groups by more than a pre-specified acceptable difference, or equivalence margin. Difference in eGFR between the q-1M and q-2M treatment groups will be assessed monthly.

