# 8. Study Population

The trial population consists of adults ≥18 years of age who are first-time transplant recipients of either living donor or deceased donor renal transplants. Patients of all races and ethnicities will be included.

This is an intention to treat, randomized, controlled trial. There will be a total of 166 subjects, randomized in equal numbers, 83 patients in each arm. We anticipate needing to consent/enroll 200 patients to achieve 166 randomized subjects accounting for an approximate 15% screen failure rate. All patients will be actively followed in the study for 12 months following enrollment. The study is projected to last 2 years.

Before any study procedures are performed, the details of the study will be described to subjects, and they will be given a written informed consent document to read. Patients who consent to participate in the study will sign and date the informed consent document in the presence of study personnel. Only patients who have given informed written consent will be included in this study.

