# 9. Study Procedures and Assessments

# See Appendix 3.

# 10. Statistical Analysis

All analyses will be conducted on the intent-to-treat (ITT) population. The distribution of continuous outcome measures will be examined, and non-parametric equivalents of the two-sample t-test will be used to assess the statistical significance of non-normally distributed outcomes.

Statistical significance of the mean difference in eGFR between the q-4 and q-8 treatment groups at 12 months post-randomization will be assessed using the two-sample independent t-test statistic. The incidence of clinically suspected or biopsy-proven acute rejection (and date of acute rejection) will be collected based upon final ETC biopsy-proven acute rejection. We will describe acute rejection rates at 6 and 12 months post-randomization for the overall cohort and for the q-1M and q-2M treatment groups by calculating time to acute rejection. Kaplan-Meier analyses examining time to acute rejection will be used for comparisons by treatment group, with the log-rank test used to assess statistical significance. Potential differences in the severity of acute rejection between the treatment groups will be assessed by comparing the proportions of grade IIA and lower rejections and grade IIB and higher rejections between the treatment groups. Statistical significance of acute rejection severity will be assessed using the two-sample independent t-test statistic.

The incidence of infection in the q-4 and q-8 treatment groups will be collected based on labs performed at regular intervals throughout the study duration. Differences in the incidence of infection by treatment group will be assessed using the two-sample t-test statistic. The incidence of death and graft loss will also be determined, and the death rate and graft loss rates will be calculated at 6 and 12 months post-randomization. Kaplan-Meier analyses examining time to death and time to graft loss will be used for comparisons by treatment group, with the log-rank test used to assess statistical significance.

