The mean eGFR at one year post-transplant for patients receiving belatacept at the Emory Transplant Center has been found to be 60.2 ml/min/1.73 m² with a standard deviation of 14.5 ml/min/1.73 m². When patients with an eGFR less than or equal to 35 ml/min/1.73 m² are excluded, the mean eGFR at one year post-transplant has been found to be 61.5 ml/min/1.73 m² with a standard deviation of 13.1 ml/min/1.73 m². Based on this inclusion criterion, the table below details several scenarios of potential sample size for different equivalence margins in order to attain 80% power for a significance level (alpha) of 0.05.

Calculated GFR is a continuous variable and will be assessed at monthly intervals (increasing to every two weeks from week 4 to 16 in the q-2M group) throughout the study. The secondary time points of rejection, death, graft lost, and HLA antibody production will be assessed at 6 and 12 months. Total cost, clinic visits, hospitalizations, biopsies and patient satisfaction will be assessed at 12 months.

Assuming a standard deviation of 13.1 ml/min/1.73 m^2:

Equivalence margin	N per group	Sample Size (total
(ml/min/1.73 m  )		N)
5.0	119	238
5.5	98	196
6.0	83	166
6.5	71	122
7.0	61	122

For example, assuming the standard deviation for eGFR at one year post-transplant is 13.1 ml/min/1.73 m^2, 166 patients total (83 per treatment group) are required to be 80% sure that a

two-sided 95% confidence interval will exclude a difference in mean eGFR between the treatment groups of more than 6.0 ml/min/1.73 m^2.

This study also aims to compare the secondary outcome of acute rejection rate between the q-1M and q-2M dosing interval groups. The one-year post-transplant acute rejection rate among patients treated with belatacept is expected to be 1-2%; based on this assumption, the table below details several scenarios of potential sample size for absolute differences in acute rejection rate in order to attain 80% power for a significance level of 0.05.

AR rate for reference group	AR rate for intervention group	Absolute difference	N per group	Sample Size
(q-4)	(q-8)	difference		(total N)
1%	4%	3%	137	274
1%	5%	4%	77	154
1%	6%	5%	49	98
1%	8%	7%	25	50
2%	5%	3%	270	540
2%	7%	5%	97	194
2%	8%	6%	68	136
2%	9%	7%	50	100

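### The primary eGFR test uses the month-12 value alone, so a missed final draw drops the patient despite monthly data; Section 3.1 should also state the 12-month time point

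*Combined protocol and SAP*

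**What the plan says.** All of this is in the combined protocol and SAP.

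- **Section 2.1 (Primary Objective)** fixes the time point. The aim is to "show that the GFR 12 months post-randomization is the same for patients who receive belatacept" on the two schedules.
- **Section 3.1 (Primary Outcome Measure)** gives none: "This study will compare the primary outcome of mean eGFR between the standard q-1M control group and the q-2M treatment group", within a margin. It then adds "Difference in eGFR between the q-1M and q-2M treatment groups will be assessed monthly".
- **Section 10 (Statistical Analysis)** names one test: the "mean difference in eGFR between the q-4 and q-8 treatment groups at 12 months post-randomization will be assessed using the two-sample independent t-test statistic". It declares all analyses intention-to-treat. A later paragraph on equivalence testing restates the primary outcome, again without a time point.
- **Section 10, sample size text**, describes measurement: "Calculated GFR is a continuous variable and will be assessed at monthly intervals", with extra two-weekly draws from week 4 to week 16 in the q-2M arm only. The schedule tables agree: the basic chemistry panel is monthly in both arms, and M1.5, M2.5 and M3.5 are marked for q-2M only.
- **Section 8 (Study Population)**: "All patients will be actively followed in the study for 12 months following enrollment". Going from 200 consented to 166 randomized covers screen failure only.

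Section 10 gives no model for the monthly eGFR values, does not label the monthly comparisons secondary or descriptive, and has no rule for a missing month-12 value.

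**The concern.** There are two linked problems.

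The first is wording. The section that defines the primary outcome should carry its time point. Section 3.2 gives one for each secondary outcome it lists, while 3.1 gives none for the primary outcome and speaks of a between-arm difference assessed every month. A reader of 3.1 alone would not know that month 12 decides the trial, or what the monthly comparisons are for.

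The second matters more. A two-sample t-test at month 12 uses one value per patient. Someone with every value through month 11 who misses the last draw is left out of the primary comparison, so the analysed set becomes those with a month-12 value and not all those randomized. The cost is lost power in a sample size that has no reserve for loss after randomization. The t-test also relies on the missing values being unrelated to renal function, a stronger condition than a model that conditions on each patient's earlier eGFR would need.

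**Working it through.** **Inputs from Section 10 and Section 8.** SD 13.1; margin 6.0; 83 per arm; 80% power; alpha 0.05.

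**Inputs not in the documents (assumed).** Fraction of month-12 values missing, m: 10%, with 5% and 20% as a range. Share of month-12 variance explained by a patient's earlier values, R²: 0.5 to 0.85. True difference zero; values missing at random.

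**Step 1: reproduce the plan's figure.** Two one-sided tests (TOST) at 0.05 per side:

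n = 2 × [13.1 × (1.645 + 1.282) / 6.0]² = 81.6, so 82 per arm by the normal formula and 83 with the t distribution.

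The t-based method also returns the table's 119, 98, 71 and 61 for the other margins. So 83 is the size for one comparison at one time point, with every randomized patient contributing a value.

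**Step 2: power with complete data.** SE = 13.1 × √(2/83) = 2.034. Normal approximation: 2Φ(6.0/2.034 − 1.645) − 1 = 2Φ(1.306) − 1 = 0.81. With the t distribution: 0.804.

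**Step 3: the t-test with 10% missing.** Observed per arm = 83 × 0.90 = 74.7. SE = 13.1 × √(2/74.7) = 2.144. Normal approximation: 2Φ(2.799 − 1.645) − 1 = 0.75. With the t distribution: 0.746.

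**Step 4: the same data with earlier values used.** When the missing values are predicted from earlier ones, the variance of an arm's month-12 mean is σ² × [(1 − R²)/n_obs + R²/n]. The effective size per arm is therefore 1 / [(1 − R²)/n_obs + R²/n].

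- R² = 0.5: 1 / (0.5/74.7 + 0.5/83) = 78.6, power 0.775.
- R² = 0.85: 1 / (0.15/74.7 + 0.85/83) = 81.6, power 0.796.

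**Step 5: is the R² range plausible?** With k earlier values and equal correlation ρ between all visits, R² = kρ² / [1 + (k − 1)ρ]. For k = 12 (M0 to M11):

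- ρ = 0.7: 5.88/8.7 = 0.68
- ρ = 0.8: 7.68/9.8 = 0.78
- ρ = 0.9: 9.72/10.9 = 0.89

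If correlation instead decays month by month from 0.7, only the last value helps and R² = 0.7² = 0.49. The range 0.5 to 0.85 covers most of this.

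**Step 6: range over the missing fraction** (TOST, 0.05 per side, t distribution, same formulas).

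| Missing at month 12 | n observed per arm | t-test power | Effective n, R² 0.5 to 0.85 | Model power |
|---|---|---|---|---|
| 0% | 83 | 80% | 83 | 80% |
| 5% | 78.9 | 78% | 80.9 to 82.3 | 79-80% |
| 10% | 74.7 | 75% | 78.6 to 81.6 | 78-80% |
| 20% | 66.4 | 67% | 73.8 to 80.0 | 74-79% |

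The first row is the limit of the argument: with no missing values, a model with arm, month and arm-by-month gives essentially the t-test's month-12 contrast.

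**The case against.** **The time point is already fixed.** This stands. A reader of 3.1 might infer that the trial could claim success at any of about 12 months, or must succeed at all of them. The documents support neither reading. The objective and the named test both say 12 months, 83 per arm reproduces as a single comparison, and nothing permits or requires success at another month. Error rates or power worked out for an any-month or every-month rule would describe a different plan. The monthly sentence may be meant only as a measurement schedule, like the similar one in the sample size text. It does, however, refer to the difference between arms and not to eGFR itself, so it still needs rewording.

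**The monthly data are used.** This stands in part. Renal function is a safety measure in Section 3.3, worsening kidney function is a recorded adverse event in Section 6.2, and abnormal laboratory values are followed up under Section 4.3.1. What is absent is an efficacy analysis of the monthly values.

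**The gain is small and rests on assumptions.** This also stands. It is nil without missing values, and neither the missing fraction nor the correlation is in the documents. Step 4 supposes that patients who miss month 12 have their earlier values; patients who leave early would contribute less. Baseline adjustment could gain more precision, but it is a separate change.

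What remains is that the plan has no allowance for loss after randomization and no missing-data rule, and that a simple alternative uses data it already collects.

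**Conclusion.** The point holds in two parts of unequal weight. Section 3.1 lacks the 12-month time point that Sections 2.1 and 10 supply; this is a minor inconsistency and does not alter the error rate of the planned test. The primary t-test discards anyone without a month-12 value although monthly eGFR exists in both arms. With an assumed 10% missing at random, that costs about 5 percentage points of power (80% to 75%), and a repeated-measures model recovers about 3 to 5 of them (to 78-80%) for R² of 0.5 to 0.85.

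These figures use TOST at 0.05 per side because that reproduces the plan's 83. Section 10 describes a two-sided 95% confidence interval, under which 83 per arm gives about 67% equivalence power even with complete data. That is a separate matter to settle.

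The change is a cheap improvement to the primary analysis. It does not correct an invalid test.

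**What to change.** 1. **Section 3.1**: state that the primary outcome is eGFR at 12 months post-randomization, and label the between-arm comparisons at other months descriptive. Add the time point where Section 10 restates the primary outcome.
2. **Section 10**: replace the t-test with a repeated-measures model of eGFR on the monthly visits common to both arms, leaving out M1.5, M2.5 and M3.5, with terms for arm, month and arm-by-month. Include every randomized patient with values at these visits. Set the month-12 contrast and its confidence interval against the 6.0 margin.

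**Cost.** One sentence in 3.1 and a short paragraph in Section 10. No new data or visits are needed, and N stays at 83 per arm. The model is slightly more complex than a t-test. It assumes that missing month-12 values are explained by earlier ones, which should be stated in the plan. That assumption does not cover values absent because of death or graft loss, which need their own stated rule.

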# 3.2 Secondary Outcome Measures

- The secondary outcome measure of rejection, death, graft lost, and HLA antibody production will be assessed at 6 and 12 months.
- Total cost, number of clinic visits, hospitalizations, and biopsies will be assessed at 12 months.

# 3.3 Safety

Patient safety will be assessed by monitoring the incidence of serious adverse events, infections, malignancies, morbidity, renal function, and rejection.

# 4. Safety Assessments

#### 4.1 Adverse Events

During the study, safety assessments will include:

- Incidence of adverse events, serious adverse events, malignancies, opportunistic infections, and premature withdrawal due to adverse events
- · Patient and Graft loss
- Changes in immunosuppressive regimen

# 4.2 Dose Adjustments of Concomitant Immunosuppression

Dose adjustment of mycophenolate mofetil or azathioprine (due to leucopenia or gastrointestinal toxicity), and prednisone may occur at the discretion of the investigator based on clinical indication.

# 4.3 Laboratory Tests

# 4.3.1 Laboratory Tests

Laboratory tests will be performed as noted in the Schedule of Events. The Emory Hospital Medical Laboratories will conduct these laboratory studies. Abnormal laboratory values will be addressed by standing protocols/operating procedures; that is through the patient's post-transplant coordinator, transplant nephrologist and/or primary nephrologist. These values will be monitored until they return to patient's baseline or other explanation is given

# 4.3.2 Biobanking and Mechanistic Studies

Samples for biobanking and mechanistic assays (e.g. CD86 saturation and belatacept peak and trough levels) will be drawn at specified intervals (see schedule of events) and stored by the Emory Transplant Clinic Biorepository. Given the possibility of the need for biological samples for unanticipated current, new and future immunologic assays, samples for this purpose may also be drawn at other times during the study period on select patients and will also be stored in the ETC biorepository. All samples will be used for assays performed by ETC investigators and Bristol-Myers Squibb. Banking of these samples is for purposes of this study, but may be used

Page 4

for other potential future research uses. Study patients will have the option of requesting for the destruction of their samples if desired.

In general, the volume of blood donated for this study will be 40 mL or 3 mL/kg, whichever is less, for each time point. Under circumstances where the needs of a specific assay require larger amounts (e.g. multiple planned assays), a larger blood volume will be considered, up to a maximum of 150 mL for any single phlebotomy session and not to exceed 3mL/kg. The total amount of blood drawn will not exceed 450 mL, or 7mL/kg whichever is less, over any 6-week period in keeping with current NIH guidelines.

# 4.4 Study stopping rules

**4.4.1** Study enrollment continuation with expedited review by the DSMB will occur for a threshold incidence of biopsy proven acute rejection of 10% on a rolling basis consistent with the following number of subjects with the event of rejection per enrolled patients (modified Simon's two-stage design strategy for 75-85% probability):

Number of subjects with Rejection (n)	Number of subjects enrolled in Q8 group
2	14
4	41
7	83

**4.4.2** Study enrollment suspension pending expedited review by the DSMB will occur for a threshold incidence of biopsy proven acute rejection of 20% on a rolling basis consistent with the following number of subjects with the event of rejection per enrolled patients (modified Simon's two-stage design strategy for 75-90% probability):

Number of subjects with Rejection (n)	Number of subjects enrolled in Q8 group
3	14
5	35
15	83

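### The Section 4.4 rejection boundaries count events against patients enrolled, with follow-up, the rolling check and the stated probabilities all undefined, so 75-85% and 75-90% are not established for the rule as written

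*Combined protocol and SAP*

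**What the plan says.** Section 4.4 has two rules for rejection in the q-2M arm (labelled Q8 there).

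- 4.4.1 (enrolment continues, with expedited DSMB review): "threshold incidence of biopsy proven acute rejection of 10% on a rolling basis", described as "modified Simon's two-stage design strategy for 75-85% probability". Boundaries: 2 of 14, 4 of 41, 7 of 83.
- 4.4.2 (enrolment suspended until expedited DSMB review): "threshold incidence of biopsy proven acute rejection of 20% on a rolling basis", described as "modified Simon's two-stage design strategy for 75-90% probability". Boundaries: 3 of 14, 5 of 35, 15 of 83.

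Both rules count the "number of subjects with the event of rejection per enrolled patients", and the table column is "Number of subjects enrolled in Q8 group". Section 1 plans on "specifically converting 6 patients per month from a q-1 month to a q-2 month schedule". Section 8 gives 83 patients per arm and 12 months of follow-up each.

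The DSMB charter, under Stopping Rules, gives other triggers for the same two actions: 5 of 10 q-2M patients for suspension and 3 of 5 for continuation with review. It does not mention follow-up either.

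**The concern.** A patient enrolled yesterday adds one to the denominator and almost nothing to the expected number of rejections. A boundary whose probability was worked out as if each patient's outcome were known will be crossed less often, or later, when many of the counted patients have only weeks of exposure. Both actions concern enrolment, so what matters most is how the rules behave while patients are still entering. If the DSMB is given 75-85% and 75-90% without the follow-up basis, it cannot tell what a boundary that has not been crossed means.

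**Working it through.** **Inputs.** Boundaries, thresholds and stated ranges: Section 4.4. Accrual of 6 per month into q-2M: Section 1. Arm size 83 and 12 months' follow-up: Section 8. Assumed, because the plan does not say: the 10% and 20% are 12-month risks, and the stated ranges are probabilities of crossing. The hazard is taken as constant unless noted.

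**Step 1: the plan's own figures.** With complete follow-up, a single boundary r of n is crossed with probability P(X ≥ r) = 1 − Σ(k<r) C(n,k) p^k (1−p)^(n−k). For 2 of 14 at 10%: 1 − 0.9^14 − 14 × 0.1 × 0.9^13 = 1 − 0.2288 − 0.3559 = 0.415.

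| Rule (true rate) | Look 1 | Look 2 | Look 3 | Any look |
|---|---|---|---|---|
| 4.4.1 (10%) | 42% | 60% | 74% | 82% |
| 4.4.2 (20%) | 55% | 86% | 71% | 91% |

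The any-look column is an exact recursion over the three cohorts (81.7% and 90.9%). It lies inside 75-85% and about one point above 75-90%, so this is the likely origin of the ranges. As single looks, only 5 of 35 falls inside its range.

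**Step 2: follow-up when the nth patient enrols.** Entry time is n/6 months. Mean follow-up is (n−1)/12 months, with each patient capped at 12.

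| n | Entry (month) | Mean follow-up (months) | Expected rejections |
|---|---|---|---|
| 14 | 2.3 | 1.1 | 0.13 at 10%; 0.28 at 20% |
| 35 | 5.8 | 2.8 | 1.78 at 20% |
| 41 | 6.8 | 3.3 | 1.18 at 10% |
| 83 | 13.8 | 6.7 | 4.71 at 10%; 9.57 at 20% |

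Expected rejections are Σ[1 − (1−p)^(f/12)] over each patient's follow-up f. The exact single-look probabilities at these moments are 0.7%, 2.9% and 19.0% (4.4.1 at 10%) and 0.2%, 3.0% and 4.8% (4.4.2 at 20%).

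**Step 3: any-look probability under each reading of the rolling check.** By simulation: 83 patients at 6 per month, constant hazard over 12 months.

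| Reading | Review at true 10% | Suspension at true 20% |
|---|---|---|
| A. Checked once, as the nth patient enrols | 20% | 7% |
| B. Each first-n cohort rechecked until enrolment closes | 58% | 80% |
| C. Each boundary applies up to its n; the last stays active to the end of follow-up | 74% | 71% |
| C, counting only crossings while enrolment is open | 20% | 8% |
| D. Each boundary stays in force until the next n, enrolment open | 74% | 97% |

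**Step 4: sensitivity of reading A.** Figures are review / suspension.

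- All rejections within 6 months of entry: about 50% / 40%, or 51% / 43% with a constant rather than uniform hazard in that window.
- All rejections within 3 months: about 67% / 71%.
- Accrual of 3, 4 or 8 per month (assumed alternatives): about 51% / 42%, 40% / 26% and 8% / 2%.

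None of these reaches the stated ranges.

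**Step 5: suspension rule at a true 10%.** With complete follow-up, the same recursion gives 32%.

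**The case against.** The strongest reply is that both rules are to be applied on a rolling basis, whereas the 20% and 7% of reading A come from three one-time checks. This stands. Reading B puts suspension at 80%, inside its stated range. Reading D puts it at 97%, although D would also suspend at 5 of 82 (6%), which fits poorly with a 20% threshold. A reader might infer that the rules are nearly silent during enrolment, or that the DSMB is being falsely reassured. The documents do not support either as a flat statement. The first is true of readings A and C but not of B and D. The second overlooks other safeguards: scheduled DSMB reviews, ad hoc review within 4 days of a request, notification of all serious adverse events, and discretionary stopping.

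It is also fair that the plan never defines the probabilities or the incidence period. Treating them as crossing probabilities and 12-month risks is an inference, though the 82% and 91% support it.

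Two further inferences should be resisted. The suspension boundaries equal 21%, 14% and 18% of patients, which might look like a mismatch with 20%. It is not an error: a boundary meant to be crossed with high probability at a true 20% will usually lie below 20%, and 5 of 35 is the one row whose single-look probability is in range. Nor does the 32% chance of suspension at a true 10% contradict the plan, which nowhere says that such a rate must not lead to suspension pending review. It is an operating characteristic that the DSMB should be shown.

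**Conclusion.** The concern holds in this form: the stated ranges correspond to complete follow-up and cumulative crossing, and Section 4.4 requires neither. With the enrolled-patient denominator at 6 per month, the chance of crossing while enrolment is open runs from about 20% to 74% for review at a true 10%, and from about 7% to 97% for suspension at a true 20%. Review falls short of 75-85% on every reading tabulated at 6 per month with constant hazard, though only just in C and D. Suspension is below, inside or above 75-90% depending on the reading.

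These figures rest on the planned accrual, an assumed 12-month risk and constant hazard; earlier rejections or slower accrual narrow the shortfall in reading A. Follow-up is not the whole explanation if the ranges were meant per look, since five of the six boundaries miss them even with complete follow-up. The documents do not show that the rules would fail in practice. They show that the rules' behaviour is not determined by the text, and the differing charter triggers add to this. It should be corrected, because these are the plan's quantified rejection triggers for the experimental interval.

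**What to change.** In Section 4.4:

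1. Define the denominator as q-2M patients with a stated minimum follow-up, plus any who rejected earlier, or express the boundary as rejections per patient-month on q-2M.
2. State the period to which the 10% and 20% incidences refer.
3. Say how the rolling check works: when counts are compared, which boundary applies between the listed values of n, and whether checking continues after enrolment closes.
4. Say whether the quoted probability is per look or cumulative. Replace 75-85% and 75-90% with operating characteristics computed on the chosen basis, including the chance of suspension at a true 10%.
5. Reconcile Section 4.4 with the Stopping Rules of the DSMB charter, so that each action has one set of triggers.

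The cost is protocol and charter wording and one short calculation. Exposure time must then be supplied with each rejection count, and the restated probabilities may look less favourable than the present ranges.
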